Note: As applicable, for early phase studies, the following sentence may be added: “Any event greater than or equal to Grade 2, please discuss with Study Physician.”

AE Adverse event; CTCAE Common Terminology Criteria for Adverse Events; NCI National Cancer Institute.

Infusion-Related Reactions

Severity Grade of the Event (Refer to NCI CTCAE applicable version in study protocol for defining the CTC grade/severity)	Dose Modifications	Toxicity Management
Any Grade	General Guidance	For Any Grade: 
– Manage per institutional standard at the discretion of investigator.– Monitor subjects for signs and symptoms of infusion-related reactions (e.g., fever and/or shaking chills, flushing and/or itching, alterations in heart rate and blood pressure, dyspnea or chest discomfort, or skin rashes) and anaphylaxis (e.g., generalized urticaria, angioedema, wheezing, hypotension, or tachycardia).
Grade 1 or 2	For Grade 1: 
The infusion rate of study drug/study regimen may be decreased by 50% or temporarily interrupted until resolution of the event.
 For Grade 2: 
The infusion rate of study drug/study regimen may be decreased 50% or temporarily interrupted until resolution of the event.
 
Subsequent infusions may be given at 50% of the initial infusion rate.
	For Grade 1 or 2: 
– Acetaminophen and/or antihistamines may be administered per institutional standard at the discretion of the investigator.– Consider premedication per institutional standard prior to subsequent doses.– Steroids should not be used for routine premedication of Grade ≤ 2 infusion reactions.
Grade 3 or 4	For Grade 3 or 4: 
Permanently discontinue study drug/study regimen.
	For Grade 3 or 4: 
– Manage severe infusion-related reactions per institutional standards (e.g., IM epinephrine, followed by IV diphenhydramine and famotidine, and IV glucocorticoid).

CTCAE Common Terminology Criteria for Adverse Events; IM intramuscular; IV intravenous; NCI National Cancer Institute.

Non-Immune-Mediated Reactions

Severity Grade of the Event (Refer to NCI CTCAE applicable version in study protocol for defining the CTC grade/severity)	Dose Modifications	Toxicity Management
Any Grade	Note: Dose modifications are not required for AEs not deemed to be related to study treatment (i.e., events due to underlying disease) or for laboratory abnormalities not deemed to be clinically significant.	Treat accordingly, as per institutional standard.
Grade 1	No dose modifications.	Treat accordingly, as per institutional standard.
Grade 2	Hold study drug/study regimen until resolution to ≤Grade 1 or baseline.	Treat accordingly, as per institutional standard.
Grade 3	Hold study drug/study regimen until resolution to ≤Grade 1 or baseline. For AEs that downgrade to ≤Grade 2 within 7 days or resolve to ≤Grade 1 or baseline within 14 days, resume study drug/study regimen administration. Otherwise, discontinue study drug/study regimen.	Treat accordingly, as per institutional standard.
Grade 4	Discontinue study drug/study regimen (Note: For Grade 4 labs, decision to discontinue should be based on accompanying clinical signs/symptoms, the Investigator's clinical judgment, and consultation with the Sponsor.).	Treat accordingly, as per institutional standard.

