APPENDIX B: STUDY CALENDAR

(A cycle = 28 days; a month = 28 days)

	Screening		Treatment/Intervention Period									End of Treatment (EOT) within 30 days of last dose	Follow Up ^s	
			Cycle 1		Cycle 2		Cycle 3	Cycle 4	Cycle 5	Cycle 6	Cycle 7- Cycle 24			
	Day -42 to Day -1	Day -14 to Day -1	Day 1 (± 3 d)	Day 15, (± 3 d)	Day 1 (± 3 d)	Day 15 (± 3 d)	Day 1 (± 3 d)	(± 7 d)						
Informed consent and research authorization/ HIPAA form ^a	X													
Demographics, medical history, histologic confirmation	X													
Physical examination, Vitals (Blood Pressure, Pulse, Temperature), weight ^b	X		X	X	X	X	X	X	X	X	X	X	X	
Height	X													
12-lead EKG	X													

Olaparib + Durvalumab
Memorial Sloan Kettering Cancer Center

c17-192

	Screening		Treatment/Intervention Period								End of Treatment (EOT) within 30 days of last dose	Follow Up ^s
			Cycle 1		Cycle 2		Cycle 3	Cycle 4	Cycle 5	Cycle 6		
	Day -42 to Day -1	Day -14 to Day -1	Day 1 (± 3 d)	Day 15, (± 3 d)	Day 1 (± 3 d)	Day 15 (± 3 d)	Day 1 (± 3 d)	(± 7 d)				
Performance status	X		X	X	X	X	X	X	X	X	X	X
Concomitant medications	X		X	X	X	X	X	X	X	X	X	X
Adverse Events	X		X	X	X	X	X	X	X	X	X	X
Radiologic evaluations and measurements ^c	X		For non-metastatic, rising PSA subjects, radiologic tests are performed at Cycle 5 (+/- 2 week), Cycle 24 (+/- 2 week) or at EOT (+/- 2 week) if discontinued sooner.								X ^d	
CBC w/ diff plts ^e		X	X	X	X	X	X	X	X	X	X	X
Comprehensive Metabolic Panel ^f		X	X	X	X	X	X	X	X	X	X	X
Coagulation Tests ^g		X										
PSA ^h		X	X		X		X	X	X	X	X	X
TFTs ⁱ		X			X			X		X	X	X
Testosterone ^j		X								X	X	
Hepatitis Panel		X										
HIV		X										
Urinalysis ^k		X										

Olaparib + Durvalumab
Memorial Sloan Kettering Cancer Center

c17-192

	Screening		Treatment/Intervention Period								End of Treatment (EOT) within 30 days of last dose	Follow Up ^s
			Cycle 1		Cycle 2		Cycle 3	Cycle 4	Cycle 5	Cycle 6		
	Day -42 to Day -1	Day -14 to Day -1	Day 1 (± 3 d)	Day 15, (± 3 d)	Day 1 (± 3 d)	Day 15 (± 3 d)	Day 1 (± 3 d)	(± 7 d)				
PBMC ^t		X		X					X		X	X
PRO-CTCAE ^m	X								X		X	X
cfDNA ⁿ		X							X			X
PDL-1 Expression (archived tissue) ^o	X											
Tissue Sequencing ^p	X											
Normal Sample ^q	X											
Olaparib Administration ^r								X				
Durvalumab Administration ^r								X				
ADT Administration ^r								X				

- a. Informed consent and radiologic assessments should be obtained within 42 days.

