Based on the severity of the imAE, durvalumab should be withheld and corticosteroids administered. Upon improvement to Grade \leq 1, corticosteroid should be tapered over \geq 28 days. More potent immunosuppressive agents such as TNF inhibitors (e.g., infliximab) should be considered for events not responding to systemic steroids. Alternative immunosuppressive agents not listed in this guideline may be considered at the discretion of the investigator based on clinical practice and relevant guidelines. With long-term steroid and other immunosuppressive use, consider need for *Pneumocystis jirovecii* pneumonia (PJP, formerly known as *Pneumocystis carinii* pneumonia) prophylaxis, gastrointestinal protection, and glucose monitoring.

Dose modifications of study drug/study regimen should be based on severity of treatment-emergent toxicities graded per NCI CTCAE version in the applicable study protocol.

AE Adverse event; CTC Common Toxicity Criteria; CTCAE Common Terminology Criteria for Adverse Events; imAE immune-mediated adverse event; NCI National Cancer Institute; NCCN National Comprehensive Cancer Network; ESMO European Society for Medical Oncology

Specific Immune-Mediated Reactions

Adverse Event	Severity Grade of the Event (NCI CTCAE version 5.0)	Dose Modifications	Toxicity Management
Pneumonitis/ Interstitial Lung Disease (ILD)	Any Grade (Refer to NCI CTCAE applicable version in study protocol for defining the CTC grade/severity)	General Guidance	
For Any Grade:
 
 Monitor subjects for signs and symptoms of pneumonitis or ILD (new onset or worsening shortness of breath or cough). Subjects should be evaluated with imaging and pulmonary function tests, including other diagnostic procedures as described below. Suspected pneumonitis should be confirmed with radiographic imaging and other infectious and disease-related aetiologies excluded and managed as described below. Initial work-up may include clinical evaluation, monitoring of oxygenation via pulse oximetry (resting and exertion), laboratory work-up, and high-resolution CT scan. Consider Pulmonary and Infectious Disease Consults.

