Grade 1	No dose modifications required. However, consider holding study drug/study regimen dose as clinically appropriate and during diagnostic work-up for other etiologies.		
For Grade 1
 
 Monitor and closely follow up in 2 to 4 days for clinical symptoms, pulse oximetry (resting and exertion), and laboratory work-up and then as clinically indicated.
Grade 2	
Hold study drug/study regimen dose until Grade 2 resolution to Grade ≤ 1.
 
If toxicity worsens, then treat as Grade 3 or Grade 4.
 
If toxicity improves to Grade ≤ 1, then the decision to reinitiate study drug/study regimen will be based upon treating physician's clinical judgment and after completion of steroid taper.
		
For Grade 2
 
 Monitor symptoms daily and consider hospitalization. Promptly start systemic steroids (e.g., prednisone 1 to 2 mg/kg/day PO or IV equivalent). Reimage as clinically indicated, consider Chest CT with contrast and repeat in 3-4 weeks If no improvement within 2 to 3 days, additional workup should be considered and prompt treatment with IV methylprednisolone 2 to 4 mg/kg/day started If no improvement within 2 to 3 days despite IV methylprednisolone at 2 to 4 mg/kg/day, promptly start immunosuppressive therapy such as TNF inhibitors (e.g., infliximab at 5 mg/kg IV once, may be repeated at 2 and 6 weeks after initial dose at the discretion of the treating provider). Caution: It is important to rule out sepsis and refer to infliximab label for general guidance before using infliximab.

			
 – Consider, as necessary, discussing with Sponsor Principal Investigator.
Grade 3 or 4	Permanently discontinue study drug/study regimen.		
 – For Grade 3 or 4 Promptly initiate empiric IV methylprednisolone 1 to 4 mg/kg/day or equivalent. – Obtain Pulmonary and Infectious Diseases Consults, consider discussing with Sponsor Principal Investigator as needed. – Hospitalize the subject. – Supportive care (e.g., oxygen). – If no improvement within 2 to 3 days, additional workup should be considered and prompt treatment with additional immunosuppressive therapy such as TNF inhibitors (e.g., infliximab at 5 mg/kg IV, may be repeated at 2 and 6 weeks after initial dose at the discretion of the treating provider). Caution: rule out sepsis and refer to infliximab label for general guidance before using infliximab.

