	Hold study drug/study regimen dose until resolution to Grade ≤ 1 or baseline		
– Perform Hepatology Consult, abdominal workup, and imaging as appropriate.
	Resume study drug/study regimen if elevations downgrade to Grade ≤ 1 or baseline within 14 days and after completion of steroid taper.		
	Permanently discontinue study drug/study regimen if the elevations do not downgrade to Grade ≤ 1 or baseline within 14 days		
	For elevations in transaminases $>8 \times$ ULN or elevations in bilirubin $>5 \times$ ULN, discontinue study drug/study regimen.		
	For Grade 4: Permanently discontinue study drug/study regimen.		

Nephritis or renal dysfunction (elevated serum creatinine)	Any Grade (Refer to NCI CTCAE applicable version in study protocol for defining the CTC grade/severity)	General Guidance	For Any Grade:
			
– Consult a nephrologist.– Monitor for signs and symptoms that may be related to changes in renal function (e.g., routine urinalysis, elevated serum BUN and creatinine, decreased creatinine clearance,

		electrolyte imbalance, decrease in urine output, or proteinuria). – Subjects should be thoroughly evaluated to rule out any alternative etiology (e.g., disease progression, infections, recent IV contrast, medications, fluid status). – Consider using steroids in the absence of clear alternative etiology even for low-grade events (Grade 2), to prevent potential progression to higher grade event.
Grade 1	No dose modifications.	For Grade 1: – Monitor serum creatinine weekly and any accompanying symptoms. 
• If creatinine returns to baseline, resume its regular monitoring per study protocol.• If creatinine worsens, depending on the severity, treat as Grade 2, 3, or 4. – Consider symptomatic treatment, including hydration, electrolyte replacement, and diuretics. – If baseline serum creatinine is elevated above normal, and there is a rise to >1 to $1.5 \times$ baseline, consider following recommendations in this row.

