Grade 2	Hold study drug/study regimen until resolution to Grade ≤ 1 or baseline. If toxicity worsens, then treat as Grade 3 or 4. If toxicity improves to Grade ≤ 1 or baseline, then resume study drug/study regimen after completion of steroid taper.	For Grade 2: – Consider symptomatic treatment, including hydration, electrolyte replacement, and diuretics. – Carefully monitor serum creatinine every 2 to 3 days and as clinically warranted. – Consult nephrologist and consider renal biopsy if clinically indicated. – If event is persistent beyond >3 to 5 days or worsens, promptly start prednisone 1 to 2 mg/kg/day PO or IV equivalent. – If event is not responsive within 3 to 5 days or worsens despite prednisone at 1 to 2 mg/kg/day PO or IV equivalent, consider additional workup. – When event returns to baseline, resume study drug/study regimen and routine serum creatinine monitoring per study protocol.
Grade 3 or 4	Permanently discontinue study drug/study regimen.	For Grade 3 or 4: – Carefully monitor serum creatinine. – Consult nephrologist and consider renal biopsy if clinically indicated. – Promptly start prednisone 1 to 2 mg/kg/day PO or IV equivalent.

		
 – If event is not responsive within 3 to 5 days or worsens despite prednisone at 1 to 2 mg/kg/day PO or IV equivalent, additional workup and prompt treatment with an immunosuppressive in consultation with a nephrologist. 	
Rash or Dermatitis (Including Pemphigoid)	Any Grade (refer to NCI CTCAE v 5.0 for definition of severity/grade depending on type of skin rash)	General Guidance	For Any Grade: 
 – Monitor for signs and symptoms of dermatitis (rash and pruritus). – Hold study drug if Stevens-Johnson Syndrome (SJS), Toxic Epidermal Necrolysis (TEN), or other severe cutaneous adverse reaction (SCAR) is suspected. – Permanently discontinue study drugs if SJS, TEN or SCAR is confirmed.
Grade 1	No dose modifications.		For Grade 1: 
 – Consider symptomatic treatment, including oral antipruritics (e.g., diphenhydramine or hydroxyzine) and topical therapy (e.g., e.g., emollient, lotion, or institutional standard).

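### Appendix G gives two restart rules for Grade 2 nephritis: one waits for the steroid taper to finish, the other does not

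*Combined protocol and SAP*

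**What the plan says.** Section 5.4.1 sends sites to Appendix G for both dose modification and toxicity management of durvalumab. Appendix G is a table with a Dose Modifications column and a Toxicity Management column, and its opening describes it as recommended guidance that is not mandatory.

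The Grade 2 row under nephritis or renal dysfunction contains three relevant instructions:

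- **Dose Modifications cell.** Drug is held until Grade 1 or less, or baseline. On that improvement, the instruction is "or baseline, then resume study drug/study regimen after completion of steroid taper".
- **Toxicity Management cell, steroid bullet.** If the event lasts beyond 3 to 5 days or worsens, the site is to "promptly start prednisone 1 to 2 mg/kg/day PO or IV equivalent".
- **Toxicity Management cell, last bullet.** "When event returns to baseline, resume study drug/study regimen and routine serum creatinine monitoring per study protocol".

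The general considerations at the head of Appendix G say that, on improvement to Grade 1 or less, "corticosteroid should be tapered over" at least 28 days. The nephritis guidance for any grade includes "Consult a nephrologist".

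**The concern.** Two cells of one row give different conditions for restarting the drug, and they conflict for a foreseeable patient: a man on prednisone for Grade 2 nephritis whose creatinine has returned to baseline before the taper has ended. The Dose Modifications cell makes him wait. The last bullet lets him restart.

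A site that acted on the bullet would give durvalumab again while the man is still immunosuppressed for an immune-mediated kidney event. The adjacent cell does not allow this. What is at stake is consistent safety handling across sites. No endpoint definition, sample size figure or analysis depends on it.

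**Working it through.** The plan states no figure on this point, so there is nothing to reproduce. The check is a comparison of text, followed by a bound on the difference in restart time.

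**The two cells side by side**

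| | Dose Modifications cell | Last Toxicity Management bullet |
|---|---|---|
| Recovery needed | Grade 1 or less, or baseline | Baseline |
| Taper condition | Taper completed | None stated |
| What resumes | Drug | Drug and routine creatinine monitoring |

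**Which men are affected**

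1. Recovered without steroids: there is no taper, so no conflict over the taper.
2. Given steroids, taper finished before baseline is reached: the bullet permits no restart during the taper.
3. Given steroids, at baseline, still tapering: the Dose Modifications cell says wait and the bullet says resume. This is the conflict.

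**Which rule was intended**

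- The Grade 2 pneumonitis row makes the restart conditional on clinical judgment "and after completion of steroid taper". The Grade 2 colitis, hepatitis and rash rows carry the same taper condition. None of these four rows has a competing restart bullet.
- The Grade 2 to 4 endocrinopathy row and the Grade 2 row for other immune-mediated reactions also state the taper condition.
- The matching bullet in the Grade 1 nephritis row deals with monitoring alone: "If creatinine returns to baseline, resume its regular monitoring per study protocol".
- The rule is not universal. The Grade 2 acute pancreatitis and Grade 2 neurotoxicity rows start steroids without stating a completed-taper condition. The point is therefore confined to the nephritis row, which states the rule in one cell and departs from it in the next.

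**Size of the gap**

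Inputs:

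- T = taper length in days, counted from improvement to Grade 1 or less; at least 28 (Appendix G, general considerations).
- d = days from Grade 1 or less to baseline; not given in the documents.
- Cycle length: "A cycle = 28 days; a month = 28 days" (Appendix B).

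The Dose Modifications cell allows a restart at day T and the bullet at day d, so

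early-restart gap = max(0, T − d).

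At the minimum taper, T = 28:

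- d = 0 (Grade 1 or less and baseline on the same day): 28 − 0 = 28 days, and 28 / 28 = 1 cycle.
- d = 14 (illustrative): 28 − 14 = 14 days, and 14 / 28 = 0.5 cycle.
- d = 28 or more: 0 days.

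The 28-day maximum holds only for the shortest permitted taper. With a longer taper the largest gap, at d = 0, equals T. The gap in days is also not a count of doses. Durvalumab is given on Day 1 of each 4-week cycle (section 6.1), so a gap shorter than 28 days may contain no scheduled infusion.

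**The case against.** The strongest reply is that the two cells can be read together: the bullet describes when recovery has occurred, and the Dose Modifications cell adds a condition for men on steroids. The bullet does not say that the taper may be ignored, and its closing reference to the protocol could be taken to cover the restart as well as the monitoring. The column heading also tells a careful reader where to look for a restart rule. For a man who recovered on hydration and diuretics alone, omitting the taper does no harm because he has none.

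That reading is sensible and probably what was meant, but it is not written down. No sentence ranks the columns, section 5.4.1 points to the appendix for both purposes, and following the bullet's reference to the protocol leads back to the same table. The bullet is not shorthand for the other cell either, since it uses a different recovery threshold.

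It is also fair to say that harm has not been shown. The documents do not establish that restarting late in a taper is dangerous. Their related discontinuation rule concerns failure to reach 10 mg or less of prednisone per day within 12 weeks, which is not a ban on any steroid use. The table is guidance and a nephrologist is involved. These points stand. They limit the importance of the inconsistency without removing it.

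**Conclusion.** The concern holds as a minor internal inconsistency in safety guidance. A steroid-treated man at baseline creatinine but still tapering receives opposite restart instructions from two cells of the same row. The other rows that state the taper condition, and the Grade 1 nephritis bullet, indicate that the taper condition is the intended rule.

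At the minimum taper, the bullet permits a restart between 0 and 28 days too early, at most one cycle. This assumes that the taper starts on improvement to Grade 1 or less, as Appendix G says, and that a site follows the bullet literally. The number of men affected cannot be estimated from the documents. With 32 subjects planned and only steroid-treated Grade 2 nephritis in question, it would be few or none.

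**What to change.** Delete the restart words from the last Toxicity Management bullet of the Grade 2 nephritis row, so that on return to baseline it resumes routine serum creatinine monitoring and nothing else. This matches the Grade 1 row and leaves the Dose Modifications cell as the single restart rule.

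An acceptable alternative is to keep the restart words and add that any steroid taper must first be complete.

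The deletion has one side effect: the bullet's stricter requirement of full return to baseline goes with it, leaving Grade 1 or less, or baseline. If the authors want full return to baseline for nephritis, they should say so in the Dose Modifications cell.

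The cost is a few words in one table cell at the next amendment, with no extra data, visits or patients.

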APPENDIX H. DOSE MODIFICATION AND TOXICITY MANAGEMENT GUIDELINES FOR OLAPARIB

Olaparib dose reductions based on hematologic nadir

Granulocytes and Platelets	Olaparib Dose Adjustment
ANC < LLN* but \geq 1000/mm3 and/or PLT < LLN but \geq 50,000/mm3 (CTCAE Grade 1-2)	Investigator judgment to continue study treatment in full dose or if dose interruption, this should be for a maximum of 4 weeks; appropriate supportive treatment and causality investigation
ANC < 1000/mm3 and/or PLT < 50,000/mm3 (CTCAE Grade 3 - 4)	Hold olaparib. Once toxicity resolves to Grade 1, olaparib may be continued -1 dose level.

*LLN = lower limit of normal

- If the ANC nadir is under 1000/mm3 (CTCAE Grade 3 - 4) and/or the platelet nadir is under 50,000/mm3 (CTCAE Grade 3 - 4) after a 1 dose level reduction of olaparib, then the next cycle will be started at -2 dose level once toxicity resolved to CTCAE Grade 1 or better
- Subjects requiring more than two dose reductions will discontinue olaparib

Management of toxicity related to olaparib

Any toxicity observed during the course of the study could be managed by interruption and/ or dose reduction of the dose if deemed appropriate by the Investigator. Olaparib must be interrupted until the subject recovers completely or the toxicity reverts to the NCI-CTCAE Grade 1 or less. If olaparib is delayed more than 8 weeks for any reason, or if a dose reduction below 200 mg daily is required, subjects will discontinue treatment with olaparib.

- Where toxicity reoccurs following re-challenge with olaparib, and where further dose interruptions are considered inadequate for management of toxicity, then the subject should be considered for dose reduction or must permanently discontinue treatment with olaparib.
- Treatment must be interrupted if any NCI-CTCAE Grade 3 or Grade 4 AE occurs which the Investigator considers to be related to administration of olaparib.

Adverse Event with Possible Relationship to Olaparib	Action to Take
Non-hematologic toxicities including nausea, vomiting, and diarrhea	Grade 1 and Grade 2 If subjects develop intolerable Grade 1 or Grade 2 toxicities (per subject) then they can undergo a dose reduction. For Grade 4 toxicities despite optimal medical therapy, hold olaparib until equal or under Grade 1. Resume at one dose level reduction. Events of nausea and vomiting are known to be associated with olaparib treatment. In study, they are generally mild to moderate (CTCAE Grade 1 or Grade 2) severity, intermittent and manageable on continued treatment. The first onset generally occurs in the first month of treatment with the incidence of nausea and vomiting not showing an increase over the treatment cycles.

		No routine prophylactic anti-emetic treatment is required at the start of study treatment; however, subjects should receive appropriate anti-emetic treatment at the first onset of nausea or vomiting and as required thereafter, in accordance with local treatment practice guidelines
General non-hematologic toxicities excluding nausea, vomiting, and diarrhea	Grade 3 or higher toxicities	Delay until recovery to Grade 1 or lower and reduce one dose level to 250mg BID). A maximum of 2 dose reductions can be made for repeat toxicity.
Anemia	CTCAE Grade 1 or Grade 2 (Hemoglobin (Hb) > 8 g/dl)	Investigate and manage as deemed appropriate by the investigator with or without interruption of study drug or change in dose, taking into account previous history of anemia. Common treatable causes of anemia (e.g., iron, vitamin B12 or folate deficiencies and hypothyroidism) should be excluded. In some cases, management of anemia may require blood transfusions.
	CTCAE Grade 3 (Hb < 8g/dl) or worse	
Study treatment should be interrupted for up to maximum of 4 weeks to allow for bone marrow recovery and the subject should be managed appropriately. Study treatment can be restarted at the reduced dose if Hb has recovered to > 10 g/dl. Any subsequently required anemia related interruptions, considered likely to be dose related, or coexistent with newly developed neutropenia, and or thrombocytopenia, will require a further study treatment dose reduction to 200 mg BID.
 
If a subject has been treated for anemia with multiple blood transfusions without study treatment interruptions and becomes blood transfusion dependant as judged by investigator, study treatment should be permanently discontinued.

Neutropenia and leukopenia	CTC Grade 3 or worse neutropenia occurs	
Manage as deemed appropriate by the investigator with close follow up and interruption of study drug. Primary prophylaxis with Granulocyte colony-stimulating factor (G-CSF) is not recommended, however, if a subject develops febrile neutropenia, study treatment should be stopped and appropriate management including G-CSF should be given according to local hospital guidelines. Please note that G-CSF should not be used within at least 24 h of the last dose of study treatment.
 
Study treatment can be restarted at the same dose if an AE of neutropenia or leukopenia have been recovered up to CTC AE Grade less than or equal to Grade 1 (ANC > 1.5 x 10⁹/L). Growth factor support should be stopped at least 24h before restarting study drug (7 days for pegylated G-CSF).
 
Any subsequent interruptions will require study treatment dose reductions to 250 mg BID as a first step and to 200 mg

		BID as a second step for a 300 mg monotherapy starting dose
Thrombocytopenia	CTCAE Grade 3 or worse	
Study treatment should be interrupted for a maximum of 4 weeks. In some cases, management of thrombocytopenia may require platelet transfusions. Platelet transfusions should be done according to local hospital guidelines.
 
Any subsequent interruptions will require study treatment dose reductions to 250 mg BID as a first step and to 200 mg BID as a second step for a 300 mg monotherapy starting dose

Prolonged hematological toxicities while on study treatment	
≥2 week interruption/delay in study treatment due to CTC Grade 3 or worse anemia and/or development of blood transfusion dependence
 
≥2 week interruption/delay in study treatment due to CTC Grade 3 or worse neutropenia (ANC < 1 x 10⁹/L)
 
≥2 week interruption/delay in study treatment due to CTC Grade 3 or worse thrombocytopenia (Platelets < 50 x 10⁹/L)
	
Weekly differential blood counts including reticulocytes (calculate reticulocyte index (RI), RI = reticulocyte count x hematocrit (Hct)/normal Hct; a value of 45 is usually used for normal Hct) (1, 2) and peripheral blood smear should be performed. If any blood parameters remain clinically abnormal after 4 weeks of dose interruption, the subject should be referred to hematologist for further investigations. Bone marrow analysis and/or blood cytogenetic analysis should be considered at this stage according to standard haematological practice.
 
Bone marrow or blood cytogenetic analysis may be performed according to standard hematological practice for subjects with prolonged hematological toxicities. Bone marrow analysis should include an aspirate for cellular morphology, cytogenetic analysis and flow cytometry, and a core biopsy for bone marrow cellularity. If it is not possible to conduct cytogenetic analysis or flow cytometry on the bone marrow aspirate, then attempts should be made to carry out the tests on a blood sample. If findings are consistent with MDS/AML, study drug should be discontinued, and a full description of findings should be submitted with an SAE report (see Section 7.3 – Reporting of SAEs for reference) to the PCCTC. Presence or absence of blood cytogenetic abnormalities and flow cytometry will be documented on the clinical database.

Pneumonitis	Suspected or any grade	If subjects present with new or worsening respiratory symptoms such as dyspnea, cough and fever, or a radiological abnormality occurs in the absence of a clear diagnosis, olaparib treatment should be interrupted and prompt investigation initiated. If pneumonitis is confirmed, olaparib treatment should be discontinued and the subject treated appropriately.
Renal Impairment	Creatinine clearance below threshold for study inclusion (51ml/min)	
If subsequent to study entry and while still on study therapy, a subject's estimated CrCl falls below the threshold for study inclusion (≥51 ml/min), retesting should be performed promptly.
 
A dose reduction is recommended for subjects who develop moderate renal impairment (calculated creatinine clearance by Cockcroft-Gault equation of between 31 and

		
50 ml/min) for any reason during the course of the study: the dose of olaparib should be reduced to 200 mg BID.
 
Because the CrCl determination is only an estimate of renal function, in instances where the CrCl falls to between 31 and 50 mL/min, the investigator should use his or her discretion in determining whether a dose change or discontinuation of therapy is warranted.
 
Olaparib has not been studied in subjects with severe renal impairment (creatinine clearance \leq 30 ml/min) or end-stage renal disease; if subjects develop severe impairment or end stage disease is it recommended that olaparib be discontinued.

--	--	--
